11.3. RANDOMISATION

Each subject will receive a screening number as soon as site staff enters the IWRS, provided by CCI, after they have signed the Informed Consent Form (ICF) at Visit 1.

The screening number will consist of a country number (2 digits), a site number (3 digits) and a unique, sequential number for a subject at an individual site (3 digits), e.g. 01-001-001. Every subject who signs the ICF must be entered into the IWRS system regardless of eligibility.

At Visit 2, eligible subjects will be randomised using the IWRS according to a pre-specified randomisation scheme such that they either receive colistimethate sodium or placebo. Site and use of stable concomitant therapy with oral macrolides (azithromycin or erythromycin or clarithromycin) (Yes/No) will be considered for balancing randomisation. Thus, within each site, subjects with azithromycin or erythromycin or clarithromycin use will be randomised independently from subjects without use of azithromycin or erythromycin or clarithromycin, to receive colistimethate sodium or placebo in a 1:1 ratio.

The randomisation within each site and nested level of azithromycin or erythromycin or clarithromycin use will be done with blocks to guarantee a good balance between colistimethate sodium and placebo at any stage of the enrolment.

Note: according to Exclusion Criterion 17, the decision on whether stable concomitant antibiotic therapy with any oral macrolides (e.g. azithromycin/erythromycin/clarithromycin) will be administered to a subject or not will have been made at least 30 days prior to Screening (Visit 1). The treatment with oral macrolides should be continued throughout the trial in order not to jeopardize the study results.

The allocation to the treatment will be stored within the IWRS database until unblinding of the trial is requested. Unblinding may be performed through the IWRS directly by the Investigators only in case of SAE of life-threatening significance where knowledge of treatment assignment is essential for the future management of patient care (see [Section 13.1](#)).

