13.1. CODE BREAKING

The code for any individual subject will not be broken by the Investigator during the course of the trial except in the circumstance of an SAE where knowledge of treatment assignment is essential for the management of patient care.

In case of emergency, unblinding of the treatment code will be done through IWRS. The treatment group will be disclosed and confirmation will follow (by fax and/or notification email). The IWRS will be designed to send a confirmation (by fax and/or notification email) to the site for every transaction performed by the site users. Site users will be provided with usernames and passwords to access the IWRS. Unblinding of the study treatment must be done in case of an emergency situation, where the Investigator considers it essential to know what treatment the subject was taking. Access to the unblinding option will be granted only to the Investigators and sub-Investigators at the sites. The IWRS will promptly notify the Sponsor and the CRA whenever a treatment code is unblinded. If the treatment code has been disclosed, this must be recorded in the eCRF.

Users from **CCI** and Sponsor Pharmacovigilance will have their own passwords to unblind subjects in case of suspected unexpected serious adverse reactions (SUSARs) to be reported to the CA and ECs.

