16.4. DEFINITION OF SERIOUS ADVERSE EVENTS OR SERIOUS ADVERSE DRUG REACTIONS

16.4.1. DEFINITION OF SERIOUS ADVERSE EVENT OR SERIOUS ADVERSE REACTION

A Serious Adverse Event (SAE) or Serious Adverse Reaction (SAR) is any untoward medical occurrence or effect that at any dose:

- results in death;
- is life-threatening (i.e. the subject was at risk of death at the time of the event/reaction; it does not refer to an event/reaction which hypothetically might have caused death if it were more severe);
- requires inpatient hospitalisation or prolongation of existing hospitalisation;
- results in persistent or significant disability/incapacity (where disability is defined as a permanent or substantial disruption of ability to carry out normal life functions, either reported or defined as per clinical judgement);

- is a congenital anomaly/birth defect;
- is an important medical event that may not result in death, be life-threatening, or require hospitalisation but, according to appropriate medical judgement, it may jeopardise the subject and may require medical or surgical intervention to prevent any of the outcomes listed in the definition above. Examples of such events include allergic bronchospasm requiring intensive treatment in an emergency room or at home, and blood dyscrasias or convulsions that do not result in hospitalisation, or development of drug dependency or drug abuse.

Any suspected transmission via a medicinal product of an infectious agent is also considered an SAE.

A Serious Adverse Reaction (SAR) is any SAE judged by either the reporting Investigator or the Sponsor as having a reasonable causal relationship to a medicinal product.

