3.8 Blinding

Investigational site staff including the Investigator and all personnel involved in study procedures will be blinded to treatment allocation. All Contract Research Organisation (CRO) and Zambon study staff involved in monitoring, data management, or other aspects of the study will also be blinded.

The allocation to treatment will be stored within the IWRS database until unblinding of the trial is requested.

The code for any individual subject will not be broken by the Investigator during the course of the trial except in the circumstance of a Serious Adverse Event (SAE) where knowledge of treatment assignment is essential for the management of patient care. CRO and Zambon Pharmacovigilance can unblind subjects in case of suspected unexpected serious adverse reactions (SUSARs) to be reported to the competent authority (CA) and ethics committees (ECs).

The randomisation code will be provided to the Biostatistics group once written authorization of database lock has been received and analysis populations have been defined.

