- Study Procedure / Subject compliance;
- Study Procedure / Unmasking (not per protocol);
- Study Procedure / Visit Missing;
- Study Procedure / Washout;
- Visit Window.

These categories may be amended or other categories may be added, but any changes will be made prior to database lock and will be documented in the Blind Data Review and Analysis Sets Report.

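### Protocol 11.3 limits Investigator unblinding through the IWRS to life-threatening SAEs, while Protocol 13.1 and SAP 3.8 permit it for any SAE where knowing the treatment is essential

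*Protocol*

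**What the plan says.** Three places state when an Investigator may break the code.

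- Protocol section 11.3 (Randomisation), last paragraph: "Unblinding may be performed through the IWRS directly by the Investigators only in case of SAE of life-threatening significance". The sentence goes on to require that knowledge of the allocation be essential for the patient's future care, and it ends with a pointer to section 13.1.
- Protocol section 13.1 (Code Breaking), first paragraph: the Investigator will not break the code "except in the circumstance of an SAE where knowledge of treatment assignment is essential for the management of patient care".
- SAP section 3.8 (Blinding): the same prohibition with the same exception, "except in the circumstance of a Serious Adverse Event (SAE) where knowledge of treatment assignment is essential for the management of patient care".

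The second paragraph of 13.1 sets out the procedure. Emergency unblinding goes through the IWRS, and "Access to the unblinding option will be granted only to the Investigators and sub-Investigators at the sites". It adds that unblinding "must be done in case of an emergency situation, where the Investigator considers it essential to know what treatment the subject was taking".

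Protocol section 16.4.1 defines an SAE. Being life-threatening is one criterion. Another is an event that "requires inpatient hospitalisation or prolongation of existing hospitalisation". A third is one that "is an important medical event that may not result in death, be life-threatening, or require hospitalisation" but may still jeopardise the subject or call for intervention.

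**The concern.** All three texts require that treatment knowledge be essential for care. Only 11.3 adds that the SAE must be life-threatening, and the word *only* turns that addition into an exclusive limit, not an example. Since the protocol's own definition makes SAE the wider term, the texts disagree about an SAE that is serious but not life-threatening.

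What is at stake is a rule for protecting patients. A site that followed 11.3 to the letter would hold back a code break that the dedicated section on code breaking allows. A rule of this kind should give the same answer wherever it is stated.

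**Working it through.** No arithmetic applies, and the plan states no figure to reproduce. The check sets the texts side by side and applies them to one case.

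**Step 1. Compare the conditions.**

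| Text | Who | Event required | Treatment knowledge essential? |
|---|---|---|---|
| Protocol 11.3 | Investigators | SAE that is life-threatening (*only*) | Yes |
| Protocol 13.1, first paragraph | Investigator | SAE | Yes |
| SAP 3.8 | Investigator | SAE | Yes |

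The sole material difference is the life-threatening qualifier in 11.3.

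**Step 2. Check that the route and users are the same.** Section 11.3 names the IWRS and the Investigators. The second paragraph of 13.1 names the IWRS as the emergency route and gives the option to Investigators and sub-Investigators. Pharmacovigilance users have separate access for SUSARs in both documents, and that access is not at issue. No other unblinding route for an Investigator is described, so the difference cannot be explained by saying that the texts govern different routes.

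**Step 3. Check that the terms differ in scope.** Under 16.4.1, meeting any one criterion makes an event an SAE. Inpatient hospitalisation suffices without risk of death, and the important-medical-event criterion expressly covers events that are not life-threatening. One example given there is allergic bronchospasm treated intensively in an emergency room or at home. Bronchospasm is also among the known effects of nebulisation listed in section 3.1.

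**Step 4. Apply the rules to a case.** Take a subject admitted to hospital with an event that is not life-threatening, where the Investigator needs the allocation to manage care.

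- Protocol 11.3: barred.
- Protocol 13.1, first paragraph: permitted.
- SAP 3.8: permitted.

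If the same event were life-threatening, all three would permit the code break. The conflict is confined to SAEs that are not life-threatening.

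**Step 5. Check whether the pointer resolves it.** Section 11.3 refers the reader to 13.1, but 13.1 does not repeat the life-threatening limit, and neither section says which prevails.

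**The case against.** The best answer is that 13.1 is the natural governing text. Section 11.3 deals with randomisation and closes with a summary sentence that sends the reader on. Section 13.1 holds the route, the users, the notifications and the recording in the eCRF. It describes no check of seriousness and no prior approval in the IWRS, so nothing there would stop a site from breaking the code. Section 13 also provides for emergency deviations for an individual subject. All of this stands, and it makes it unlikely that a site would stop at 11.3 and withhold a code break. It does not remove the word *only*, and the documents contain no rule of precedence.

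Four stronger readings are tempting, and the documents do not support them.

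- *That 11.3 forbids what 13.1 requires.* The mandatory wording is in the second paragraph of 13.1, which speaks of an emergency and does not mention an SAE. Applying it to these events is an interpretation. The firm conflict is between barred and permitted.
- *That a code break made under 13.1 would be logged as a major deviation.* SAP 4.10.1 lists a category "Study Procedure / Unmasking (not per protocol", but this is a label without a criterion, nothing ties it to 11.3, and exact definitions are left to the blind review meeting. Once 11.3 matches 13.1, such a code break is plainly per protocol.
- *That counting the SAE criteria that 11.3 leaves out measures the gap.* The criteria in 16.4.1 overlap: a hospitalised event may also be life-threatening. A count of criteria says nothing about the share of SAEs affected.
- *That the withdrawal rule is drawn in.* Protocol section 14 and SAP 3.6 list non-emergency unblinding as a reason for withdrawal. That rule turns on whether there was an emergency, a test that 11.3 does not use.

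**Conclusion.** The inconsistency is real and sits in the operative text. Protocol 11.3, taken literally, bars an Investigator code break for an SAE that is not life-threatening, while Protocol 13.1 (first paragraph) and SAP 3.8 permit it when treatment knowledge is essential. This rests on the ordinary meaning of *only* and on the SAE definition in 16.4.1; it needs no assumption about event rates.

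Its size is one phrase and one class of event. The documents give no expected number of code breaks, so no frequency can be attached. A reader might infer some effect on the results, but the documents give no ground for one: power, alpha and the primary analysis are untouched. It is a minor correction, justified because it concerns patient safety.

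**What to change.** In Protocol 11.3, delete the life-threatening qualifier, which is the last three words of "Unblinding may be performed through the IWRS directly by the Investigators only in case of SAE of life-threatening significance". The sentence then asks for an SAE where treatment knowledge is essential, as 13.1 (first paragraph) and SAP 3.8 already do.

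No change is needed to 13.1, SAP 3.8, SAP 4.10.1 or the withdrawal rule. The second paragraph of 13.1 would still refer to an emergency without naming an SAE; that is a separate wording difference and this correction does not depend on it.

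The cost is one phrase in a written protocol amendment under section 12. It needs no extra data and no change to the sample size or any analysis.

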11.4. INVESTIGATIONAL MEDICINAL PRODUCT ACCOUNTABILITY

IMP inventory and accountability records will be maintained within IWRS. The following rules are to be followed:

- a) The Investigator will keep IMP in a pharmacy, or a locked and secure storage facility, accessible only to those individuals authorised by the Investigator to dispense the IMP.
- b) The inventory will be maintained by the Investigator or pharmacist or other nominated individual. A Site Inventory Summary Report will be printed from IWRS and signed by the Investigator or pharmacist and Clinical Research Associate (CRA) and filed in the Investigator Site File and/or Pharmacy Site File.
- c) The IWRS includes details of IMP received and a clear record of when they were dispensed and to which subject and returned IMP and when returned. The IWRS shall indicate the quantity and description of all IMPs on hand at any time during the course of the clinical trial.
- d) At the conclusion or termination of the clinical trial, the Investigator agrees to conduct a final IMP inventory and to record the results of the inventory on an appropriate form provided by the CRO/IWRS (Investigational Product Return Form). The pharmacist, if applicable, may assist with this. The monitor will check that IMP accountability was correctly performed. According to instructions, the Investigator will return all original IMP containers, whether empty or containing test preparations, to for final reconciliation and destruction.
- e) The IMP can be dispensed to subjects only by the Investigator/pharmacist who agrees not to supply IMP to any person except those named as Investigators/Co-Investigators/study coordinators as detailed in the Site Signature/Delegation Log, and to subjects in this trial.

12. CLINICAL TRIAL AMENDMENTS

Changes to the CTP can only be made by preparing written amendments to be agreed and signed by the Investigator and Sponsor. No substantial amendment can be implemented without a favourable opinion of the EC and CA, unless the changes consist of urgent safety measures to protect trial subjects.

Amendments which are non-substantial amendments as defined by current regulations can be sent to the EC/CA for notification as applicable per local requirements, and may be implemented at the site before EC notification according to local rules.

13. DEVIATIONS FROM THE CLINICAL TRIAL PROTOCOL

Any major or critical deviation which may have an impact on study results and/or the safety of the subjects should be immediately reported to the CRO and a decision will be taken together with the Sponsor whether or not the subject (for whom the deviation from the CTP took place) is to continue in the trial. A deviation log will be maintained to track actual deviations and decisions taken, including all deviations which occurred. All deviations will be reported to the EC and CA according to ICH-GCP and local requirements.

In case of an emergency deviation from the CTP applicable only when an emergency situation has to be faced for a subject, this deviation will only be applied to that individual.

In such an emergency the Investigator must contact the CRO by telephone as soon as possible.

13.1. CODE BREAKING

The code for any individual subject will not be broken by the Investigator during the course of the trial except in the circumstance of an SAE where knowledge of treatment assignment is essential for the management of patient care.

In case of emergency, unblinding of the treatment code will be done through IWRS. The treatment group will be disclosed and confirmation will follow (by fax and/or notification email). The IWRS will be designed to send a confirmation (by fax and/or notification email) to the site for every transaction performed by the site users. Site users will be provided with usernames and passwords to access the IWRS. Unblinding of the study treatment must be done in case of an emergency situation, where the Investigator considers it essential to know what treatment the subject was taking. Access to the unblinding option will be granted only to the Investigators and sub-Investigators at the sites. The IWRS will promptly notify the Sponsor and the CRA whenever a treatment code is unblinded. If the treatment code has been disclosed, this must be recorded in the eCRF.

Users from **CCI** and Sponsor Pharmacovigilance will have their own passwords to unblind subjects in case of suspected unexpected serious adverse reactions (SUSARs) to be reported to the CA and ECs.

14. CLINICAL TRIAL WITHDRAWALS/DROP-OUTS

Subjects will be withdrawn from the trial for one of the following reasons:

- subject may withdraw from the study at any time at his/her own request;
- subject may withdraw from the study due to an AE including subjects experiencing a decrease in FEV₁ >15% from pre-bronchodilator baseline and/or clinically determined bronchospasm after receiving their first dose of IMP;
- subject may be withdrawn at any time at the discretion of the Investigator for safety, behavioural, compliance or administrative reasons;
- subject may be withdrawn due to lack of adherence to study medication regimen.
- subjects who become pregnant should be withdrawn from the trial (subject's follow-up should be performed in accordance with [Section 16.9](#));
- non-emergency unblinding of study treatment allocation;
- lost to follow up: before a subject is deemed lost to follow up, the Investigator or designee must make every effort to regain contact with the participant (where possible, 3 telephone calls and, if necessary, a certified letter to the participant's last known mailing address or local equivalent methods). These contact attempts should be documented in the participant's medical record. Should the participant continue to be unreachable, he/she will be considered to have withdrawn from the study;
- Sponsor, CA, or EC, terminate the trial or participation of an individual site.

The reason for removal of a subject from the trial or premature discontinuation of treatment must be fully documented in the eCRF as well as in respective source documents. Follow-up for withdrawn subjects follows the procedures described in [Section 16.8](#) and [Section 16.9](#). If possible, the subject should return to the clinic for an early End of Study Visit. The subject must return the medications, **CCI**, and details regarding AEs (including exacerbations) and concomitant medications will be collected.

15. STOPPING AND DISCONTINUATION CRITERIA FOR THE TRIAL

The trial may be prematurely terminated or placed on temporary hold for the following reasons:

- the Sponsor feels that the number and/or severity of AEs justifies discontinuation of the trial;
- the Sponsor considers the applied doses of the IMP to be no longer relevant;
- data not known before become available and raise concern about the safety of the IMP so that continuation would pose potential risks to the subjects.

Premature termination of the trial must be reported to the EC and CA according to applicable laws; generally within 15 days. A detailed written explanation of the reason should be given and alternative procedures for subjects under treatment specified.

However, trial results have to be reported according to the requirements outlined in this CTP as far as applicable.

If, after the termination of the trial, the risk/benefit analyses have changed, the new evaluation should be provided in case it will have an impact on the planned follow-up of the subjects who have participated in the trial. If possible, the subject should return to the clinic for an early End of Treatment Visit.

16. REPORTING SAFETY INFORMATION

16.1. DEFINITION OF ADVERSE EVENT

An AE is "any untoward medical occurrence in a patient or clinical trial subject administered a medicinal product and which does not necessarily have a causal relationship with this treatment".

AEs include:

- worsening (change in nature, severity or frequency) of conditions present at the onset of the trial;
- subject deterioration due to the primary illness;
- intercurrent illnesses;
- drug interactions;
- events related or possibly related to concomitant medications;
- abnormal laboratory values, as well as significant shifts from baseline within the range of normal, which the Investigator considers to be clinically significant.

An AE can therefore be any unfavourable and unintended sign (including an abnormal laboratory finding), symptom, or disease temporally associated with the use of an IMP, whether or not considered related to the IMP.

16.2. DEFINITION OF ADVERSE EVENT OF SPECIAL INTEREST

No AEs of special interest are defined for this trial.

16.3. DEFINITION OF ADVERSE DRUG REACTION

An adverse drug reaction (ADR) is “any untoward and unintended response to an IMP related to any dose administered and which implies an AE with at least a reasonable possibility of a causal relationship with the use of the product (i.e. there is evidence or arguments to suggest a causal relationship).

The definition also covers medication error and uses outside what is foreseen in the CTP, including misuse and abuse of the IMP.

All AEs judged by either the reporting Investigator or the Sponsor as having a reasonable causal relationship to a medicinal product qualify as suspected ADRs.

16.3.1. DEFINITION OF UNEXPECTED ADVERSE DRUG REACTION

An unexpected ADR is: “An adverse reaction, the nature, or severity of which is not consistent with the applicable product information”.

The reference safety information for evaluation of AE expectedness in this trial will be Section 7.5.9 of the Investigator’s Brochure for colistimethate sodium in line with relevant information of the current EU SmPC Promixin® 1 MIU powder for nebuliser solution. In this patient population, pulmonary exacerbations (including pneumonia) are also considered as expected adverse events.

